11.5 Other Safety Parameters

11.5.1 Immunogenicity Assessments

Blood samples will be collected from all participants prior to dosing on day 1 and at the day 30 and day 90 follow-up visits. A 2-tier assay approach will be used for the detection of binding and neutralizing antibodies to AGN-151607 in human serum.

Immunogenicity findings (positive) will be tabulated with the number and percentage of participants at each visit separately for each AGN-151607 treatment group. Percentages will be based on the number of treated participants with interpretable antibody assays in each treatment group at the specified visit. A cumulative summary based on positive findings at any visit will be done for each AGN-151607 treatment group.

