#### AGN-151607

Objectives	Endpoints					
Secondary	Secondary Efficacy					
To compare the efficacy of AGN-151607 with placebo to prevent POAF using alternative definitions for AF in participants who are undergoing open-chest cardiac surgery	
 
Percentage of participants with at least 1         continuous AF episode ≥ 2 minutes during the first         30 days post-surgery
 
Percentage of participants with at least 1         continuous AF episode ≥ 5 minutes during the first         30 days post-surgery
 
Percentage of participants with at least 1         continuous AF episode ≥ 30 minutes during the         first 30 days post-surgery
 
Percentage of participants with at least 1         continuous AF episode ≥ 30 minutes during the         first 30 days post-surgery
 
Percentage of participants with at least 1         continuous AF episode ≥ 1 hour during the first         30 days post-surgery
 
Percentage of participants with at least 1         continuous AF episode ≥ 4 hours during the first         30 days post-surgery
 
Percentage of participants with at least 1         continuous AF episode ≥ 6 hours during the first         30 days post-surgery
 
Percentage of participants with at least 1         continuous AF episode ≥ 12 hours during the first         30 days post-surgery
 
Percentage of participants with at least 1         continuous AF episode ≥ 12 hours during the first         30 days post-surgery
 
Percentage of participants with at least 1         continuous AF episode ≥ 12 hours during the first         30 days post-surgery
 
					
Safety	Safety Assessments					
• To compare the safety of AGN-151607 with placebo in participants undergoing open-chest cardiac surgery	
 
Adverse events (AEs), physical examination, clinical laboratory tests, vital signs, electrocardiogram (ECGs), pulmonary function
 
Potential immunogenicity response
 
					

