#### 8.2.7. Immunogenicity Assessments

Blood samples will be collected from all participants prior to dosing on Day 1 and at the Day 30 and Day 90 follow-up visits. A 2-tier assay approach will be used for the detection of binding and neutralizing antibodies to AGN-151607 in human serum. In tier 1, serum samples will be screened using a validated enzyme-linked immunosorbent assay (ELISA). The positive samples will subsequently be immune depleted to confirm that the antibodies were specifically binding to AGN-151607 and then titered to assess the magnitude of antibodies present. In tier 2, only samples that are considered positive in the ELISA will be tested for neutralizing antibodies to AGN-151607 using a validated assay.

Samples may be stored for a maximum of 2 years (or according to local regulations) following the last participant's last visit for the study at a facility selected by the sponsor to enable further analysis of immune responses to AGN-151607.

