5.3 Safety Objectives

• To compare the safety of AGN-151607 with placebo in participants undergoing open-chest cardiac surgery.

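### The cumulative antibody summary in SAP 11.5.1 has no baseline condition and no placebo column, so it cannot separate pre-existing antibody from antibody that appears after dosing

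*SAP*

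**What the plan says.** **Sampling.** SAP 11.5.1 states: "Blood samples will be collected from all participants prior to dosing on day 1 and at the day 30 and day 90 follow-up visits". Protocol 8.2.7 gives the same rule, so placebo participants are sampled too.

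**By-visit table.** SAP 11.5.1 tabulates positives as the number and percentage of "participants at each visit separately for each AGN-151607 treatment group". The denominator is given per visit: "Percentages will be based on the number of treated participants with interpretable antibody assays in each treatment group at the specified visit".

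**Cumulative table.** "A cumulative summary based on positive findings at any visit will be done for each AGN-151607 treatment group". No denominator is given for this one.

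**Purpose.** The safety objective in SAP 5.3 is "To compare the safety of AGN-151607 with placebo in participants undergoing open-chest cardiac surgery". Protocol Section 3 and the synopsis list "Potential immunogenicity response" among the assessments under that objective.

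**Assay.** Protocol 8.2.7 describes a two-tier approach: an ELISA screen, then "The positive samples will subsequently be immune depleted to confirm that the antibodies were specifically binding to AGN-151607", then titration. Only ELISA-positive samples go on to the neutralizing assay.

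**The concern.** An immunogenicity table is normally read to learn how many treated participants developed antibody after exposure. That needs each participant's post-dose result set against the pre-dose result. The cumulative rule does not ask for this. A participant positive only before injection meets it, and so does one who was positive before injection and stayed positive unchanged.

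Pre-existing antibody is possible in this population. Exclusion 2.02 and Table 6-2 of the protocol bar botulinum toxin use in the previous 6 months, so earlier users may enrol. Exclusion 2.03 removes immunized participants, but only as far as the medical history shows it.

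At stake is the interpretation of a safety endpoint for a product whose adverse event profile, by Protocol 2.3, is not yet fully characterized in humans. No test or decision depends on the table.

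**Working it through.** The documents state no antibody rate, so there is no figure to reproduce. The check has two parts.

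**1. The rule beside the plan's other safety rules**

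| Item | Baseline handling | Arms |
|---|---|---|
| Adverse events (SAP 11.1) | Must begin or worsen on or after injection | All |
| Laboratory values of potential clinical significance (SAP 11.2) | Participants already abnormal at baseline leave both numerator and denominator | All |
| Vital signs and ECG of potential clinical significance (SAP 11.3, 11.4) | Post-baseline values only | All |
| Pulmonary function (SAP 11.5.2) | Change from baseline | All three |
| Antibody, cumulative (SAP 11.5.1) | None stated | Active arms only |

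The general baseline rule in SAP 11.0 (Protocol 9.4.2) covers physical examination, laboratory, vital signs and ECG. It does not name immunogenicity, so it does not fill the gap. Neither document defines a treatment-emergent or boosted antibody response.

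**2. Illustration of size**

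Inputs:
- Participants per arm: 330 / 3 = 110 (330 randomized 1:1:1, Protocol 4.1 and SAP 13.0).
- Pre-dose prevalence b: **assumed**, 1% to 5%.
- Residual false-positive rate per sample after confirmation, f: **assumed**, 0 to 2%, independent between samples.
- No drug effect; pre-existing antibody persists at all three samples.

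With f = 0, the number counted per arm because of pre-existing antibody is 110 × b:
- b = 1%: 110 × 0.01 = 1.1
- b = 5%: 110 × 0.05 = 5.5

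So about 1 to 6 per arm. At b = 1%, the chance of at least one such participant in an arm of 110 is 1 − 0.99^110 = 0.67.

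Allowing for false positives:
- Any-visit rate = b + (1 − b) × (1 − (1 − f)³)
- Rate when a negative pre-dose sample is required = (1 − b) × (1 − f) × (1 − (1 − f)²)

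Example, b = 2% and f = 1%: 0.02 + 0.98 × 0.0297 = 0.0491, or 5.4 of 110; against 0.98 × 0.99 × 0.0199 = 0.0193, or 2.1 of 110.

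| b | f | Any visit, of 110 | Pre-dose negative and post-dose positive, of 110 |
|---|---|---|---|
| 1% | 0 | 1.1 | 0 |
| 2% | 0 | 2.2 | 0 |
| 5% | 0 | 5.5 | 0 |
| 0 | 1% | 3.3 | 2.2 |
| 2% | 1% | 5.4 | 2.1 |
| 5% | 2% | 11.6 | 4.1 |

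The baseline condition removes the pre-existing positives. It leaves most of the false positives, and the placebo column is what would show how many of those to expect after dosing.

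**The case against.** **The word visit may mean only the follow-up visits.** The sampling sentence attaches it to Day 30 and Day 90, and on that reading the pre-dose sample is not in the cumulative count. The ambiguity is real. However, SAP Table 15-1 lists baseline as a scheduled visit for safety analyses, and the schedules place the first serum sample at Visit 1. The narrow reading also does not cure the problem: persistent antibody would still be positive at Day 30 and still be counted, and the by-visit table would then lose its pre-dose row.

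**Pre-dose prevalence is already visible.** If the pre-dose sample is a visit, the by-visit table gives its prevalence in both active arms. This stands, and a reader who concluded that there is no background rate at all would be going too far. What is missing is the link within participants and the placebo rate after dosing.

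**The design limits the problem.** Immune depletion reduces false positives, and exclusions 2.02 and 2.03 reduce pre-existing antibody. Both points stand. Depletion confirms binding specificity, though, and does not tell old antibody from new.

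**The SAP does not attribute the positives to the drug.** A reader might infer that pre-existing antibody will be reported as a drug response. The text does not support that: it speaks only of positive findings. Nor does it support a stated fold inflation. With an assumed 1% induced rate and 1% to 5% baseline, the ratio is (1 + 1)/1 to (1 + 5)/1, or 2 to 6; with an assumed 5% induced rate it is (5 + 1)/5 to (5 + 5)/5, or 1.2 to 2. Both terms are assumptions, so no such multiplier should be quoted.

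**Table specifications are in a separate document** (SAP 4.0). Participant-level antibody listings may exist. They would help a reader, but would not change the rule in the SAP.

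**Conclusion.** The point holds as a limit on interpretation: as written, the cumulative antibody count cannot separate pre-existing antibody from antibody that appears after dosing, and the placebo samples that would give a concurrent background are not tabulated. The size is unknown. At an assumed pre-dose prevalence of 1% to 5% it is about 1 to 6 of 110 per arm. That is an upper figure for the excess from this source, because a pre-dose positive with a genuine titre rise would properly count. If no one is positive pre-dose, pre-existing antibody adds nothing. Severity is minor: the table is descriptive, and the efficacy analyses are unaffected.

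**What to change.** Amend SAP 11.5.1 as follows:

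1. Base the cumulative summary on Day 30 and Day 90. Count participants who are negative pre-dose and positive at either time, plus those positive pre-dose who show a pre-specified titre rise.
2. Use as denominator the treated participants with an interpretable baseline assay and at least one interpretable post-dose assay. The schedule of activities allows serum collection to be omitted with sponsor approval, so missing samples are foreseeable.
3. Keep pre-dose prevalence as a separate row.
4. Add the placebo column to both tables.
5. Reconcile the baseline draw. The schedules in both documents mark it at Screening, while Protocol 8.2.7 and SAP 11.5.1 place it before dosing on Day 1.

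The cost is a short wording change and a revised table layout. Titres are already planned under Protocol 8.2.7, and placebo serum is already collected. The only added expense would be assaying the placebo samples, if that is not already planned.

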11.5.2 Pulmonary Function Test (PFT)

Study participant pulmonary function will be assessed at the screening and day 30 visits using forced procedures and compared across all 3 study groups. To demonstrate reproducibility of results, participants will be required to perform at least 3 acceptable spirometry maneuvers up to a maximum of 8 attempts. The results of all respiratory measures will be reviewed for clinically significant findings.

The assessments will include the following:

- 1. Forced vital capacity (FVC) measured from a maximal forced exhalation
- 2. Forced expiratory volume (FEV) in 1 second (FEV₁), 3 seconds (FEV₃) and 6 seconds (FEV₆)
- 3. FEV_1/FVC ratio

The average and the maximum of the measurements recorded on the eCRF for each of the PFT parameters (FVC, FEV1, FEV3, FEV6, and FEV₁/FVC ratio) at each visit will each be used in the data analysis. Descriptive statistics for each PFT parameter and changes from baseline values at each assessment time point will be presented by treatment group.

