# 8.2.5. Pulmonary Function Testing

Study participant pulmonary function will be assessed at the screening visit and Day 30 using forced procedures and compared across all 3 study groups (refer to study reference guide). Note, if local policies contraindicate or prohibit PFT assessments due to potential for viral spread or microbial precautions, then the PFT is not required after explicit approval from the sponsor. If PFT assessments are not prohibited by local regulations/policies, then the PFTs should be conducted.

Spirometry testing will be conducted by a pulmonologist, pulmonary technician, respiratory therapist, nurse, and/or other appropriate personnel trained in this procedure, following the American Thoracic Society (ATS) Standardization of Spirometry guidelines (Miller, 2005). To demonstrate reproducibility of results, participants will be required to perform at least 3 acceptable spirometry maneuvers up to a maximum of 8 attempts. The results of all respiratory measures will be reviewed for clinically significant findings.

The assessments will include the following:

- 1. Forced vital capacity (FVC) measured from a maximal forced exhalation
- 2. Forced expiratory volume (FEV) in 1 second (FEV1), 3 seconds (FEV3) and 6 seconds (FEV6)

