		• Updated that TEAEs would be sorted based on descending frequency of total percentage across treatment groups and not just descending frequency in the AGN-151607 250 U arm;	
		• Added FEV ₁ /FVC ratio and maximum of measurements to analysis of PFT parameters in Section 11.5.2 to reflect parameters analyzed in other studies of botulinum toxins;	
		• Removed cardiac pacemaker insertion from list of procedures of interest due to atrial fibrillation or atrial flutter in Section 8.0 (at time of SAP amendment, no such procedures were marked as due to atrial fibrillation or atrial flutter);	
		• Added description of datetime adjustment for ePatch analyses to correct for instances of internal clock resets as Section 15.8.	

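### SAP 11.5.2 takes the maximum of the FEV1/FVC ratio as if it were a volume; if ratios are formed per manoeuvre, the result is biased upward and usually comes from a shorter exhalation

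*SAP*

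**What the plan says.** SAP 11.5.2 lists FVC ("Forced vital capacity (FVC) measured from a maximal forced exhalation"), FEV1, FEV3 and FEV6, and adds "FEV_1/FVC ratio" as a third assessment. One rule covers all five: "The average and the maximum of the measurements recorded on the eCRF for each of the PFT parameters" at each visit go into the analysis. On the number of efforts, "participants will be required to perform at least 3 acceptable spirometry maneuvers up to a maximum of 8 attempts". Testing is at screening and Day 30, and the output is descriptive: "Descriptive statistics for each PFT parameter and changes from baseline values at each assessment time point will be presented by treatment group".

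Protocol 8.2.5 has the same four volumes, no ratio, and requires trained staff working to the "American Thoracic Society (ATS) Standardization of Spirometry guidelines". According to SAP 17.0, Amendment 2 added the ratio and the "maximum of measurements to analysis of PFT parameters in Section 11.5.2", so that the analysis matches parameters used in other botulinum toxin studies.

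Neither document says whether the ratio is formed within each manoeuvre or from the best FEV1 and best FVC, or how many manoeuvres are entered on the eCRF.

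**The concern.** Taking the maximum is sound for FVC, FEV1, FEV3 and FEV6, because poor effort can only make a volume smaller. The ratio behaves differently. A manoeuvre stopped early has a smaller FVC and therefore a larger FEV1/FVC. The maximum of several ratios also exceeds their mean simply because it is the largest of several variable values.

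Pulmonary function is a named safety assessment (Protocol 3 and 9.4.2). The adverse event of special interest is possible distant spread of toxin, whose term list in SAP 11.1 includes diaphragmatic paralysis and respiratory failure. The only scheduled post-dose spirometry is at Day 30, after open-chest surgery. If participants stop exhaling sooner at Day 30 than at screening, the maximum ratio would move upward and could be read as stable or better function.

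**Working it through.** The plan states no figure for this summary, so there is none to reproduce. All variability inputs below are assumptions.

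**1. Selection effect alone.** For k independent normal values, the expected maximum exceeds the mean by 0.85 SD (k = 3), 1.16 SD (k = 5) and 1.42 SD (k = 8). From the documents, at least 3 manoeuvres must be acceptable and 8 is the cap on attempts. The number that enters the maximum is not stated.

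**2. One-sided shortfall model.** Assumed true FEV1 2.4 L and true FVC 3.2 L, so the true ratio is 2.4 / 3.2 = 0.75. For each manoeuvre, FEV1 = 2.4 × (1 − |e1|) and FVC = 3.2 × (1 − |e2|), with e1 and e2 normal, mean 0, SD equal to the stated scale. There were 200,000 simulated sessions per row, with no acceptability filter.

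| k | FEV1 / FVC scale | Maximum ratio | Average ratio | Largest FEV1 / largest FVC | Maximum came from smallest FVC |
|---|---|---|---|---|---|
| 3 | 2% / 3% | 0.771 | 0.756 | 0.753 | 77% |
| 3 | 2% / 8% | 0.829 | 0.791 | 0.766 | 90% |
| 3 | 4% / 3% | 0.763 | 0.744 | 0.748 | 63% |
| 3 | 4% / 8% | 0.818 | 0.778 | 0.761 | 82% |
| 8 | 2% / 3% | 0.783 | 0.756 | 0.751 | 71% |
| 8 | 2% / 8% | 0.864 | 0.791 | 0.757 | 88% |
| 8 | 4% / 3% | 0.776 | 0.744 | 0.749 | 55% |
| 8 | 4% / 8% | 0.853 | 0.778 | 0.754 | 78% |

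Maximum minus average runs from 0.771 − 0.756 = 0.015 to 0.818 − 0.778 = 0.040 at k = 3, and from 0.783 − 0.756 = 0.027 to 0.853 − 0.778 = 0.075 at k = 8.

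**3. What happens when effort changes (same model, k = 3).**
- More early stopping (FVC scale 3% to 8%, FEV1 scale held at 2%): the maximum rises by 0.829 − 0.771 = 0.058, the average by 0.791 − 0.756 = 0.035, and largest/largest by 0.766 − 0.753 = 0.013.
- Weaker start (FEV1 scale 2% to 8%, FVC scale held at 3%): the maximum falls from 0.771 to 0.751.
- A further loss that scales both volumes equally: it cancels in the quotient, so the maximum stays at 0.771.

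**4. Second model as a check.** True FEV1 2.25 L and FVC 3.0 L (ratio 0.75), FEV1 CV 2%, FVC CV 1%, and an exponentially distributed FVC loss from early stopping. As the mean loss goes from 0% to 10%:
- maximum ratio: 0.765 to 0.897 (k = 3) and 0.774 to 0.953 (k = 8), a drift of +0.13 and +0.18;
- average ratio: 0.750 to 0.831;
- largest/largest: 0.757 to 0.790 (k = 3) and 0.761 to 0.780 (k = 8), a drift of +0.03 and +0.02.

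Across scenarios with early stopping, and with FEV1 CV at 2% or 4%, the maximum came from the least complete exhalation in 48% to 88% of sessions. The direction agrees with step 2; the sizes depend on the assumptions.

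**The case against.** A reader might infer that the maximum always picks out the least complete exhalation, that it rises whenever effort worsens, and that it would therefore hide respiratory harm. None of the three is supported.

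- FEV1 variation also drives the maximum, so it often comes from a different manoeuvre (steps 2 and 4).
- The direction depends on how effort fails (step 3). The documents contain no data on spirometry effort after sternotomy.
- Loss of FVC is reported in its own right, as average and as maximum with change from baseline. Respiratory results are reviewed for clinically significant findings, and the respiratory terms for distant spread are tabulated separately.

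Other points against:
- The acceptability requirement should exclude many truncated efforts, and the simulations do not model it. Eight is a limit on attempts, not a count of usable manoeuvres.
- The same rule applies at both visits and in all three blinded arms, so part of the bias cancels in change from baseline and between groups unless effort or the number recorded differs by visit or arm.
- The average ratio is reported too.
- Amendment 2 gives comparability with other studies as its reason.

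Most of this stands, and it limits the consequence. It does not remove the defect. The SAP names the ratio under the maximum rule, and nothing else in either document defines it. The average is only a partial safeguard because it also rises with early stopping. If best FEV1 over best FVC was intended, the SAP does not say so.

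**Conclusion.** The point holds as a minor defect in a stated derivation. If ratios are formed per manoeuvre, their maximum overstates the session average, increasingly so with more recorded manoeuvres, and tends to come from shorter exhalations. Under the step 2 assumptions it averages 0.763-0.829 with 3 manoeuvres and 0.776-0.864 with 8, against a true 0.75; largest/largest over the same inputs gives 0.748-0.766 and 0.749-0.757. These sizes rest on assumed variability, an assumed count and no acceptability filter. If the eCRF holds only one best-effort ratio per visit, the problem does not arise, but the documents do not establish that.

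The consequence is confined to one descriptive safety summary with no test and no threshold for the ratio. A claim that the rule conceals loss of pulmonary function would go too far, since FVC and FEV1 are shown directly.

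**What to change.** In SAP 11.5.2, replace the maximum of ratios by a single derivation: at each visit, FEV1/FVC is the largest FEV1 divided by the largest FVC among the acceptable manoeuvres, which need not be the same manoeuvre. Keep the maximum for FVC, FEV1, FEV3 and FEV6. The average of the per-manoeuvre ratios may stay if it is labelled supplementary.

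This takes one sentence and one programmed variable. It needs no new data provided FEV1 and FVC are recorded for each manoeuvre, which the average-and-maximum rule implies. There are two costs. Comparability is reduced if the other botulinum toxin studies mentioned in SAP 17.0 used the maximum ratio. The replacement also still drifts slightly upward with early stopping, though much less (step 4: +0.03 against +0.13 at k = 3, and +0.02 against +0.18 at k = 8).

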# 9. Statistical Considerations

# 9.1. Statistical Hypotheses

In general, continuous variables will be summarized by descriptive statistics and will include sample size, mean, standard deviation, median, minimum, and maximum. Nominal variables will be summarized by frequency and percentage. Continuous variables will be analyzed using 2-sample t-test or analysis of variance (ANOVA) techniques for comparisons between treatment groups, and paired t-tests for within-group comparisons. Ordinal variables will be analyzed using Wilcoxon rank-sum or Cochran-Mantel-Haenszel (CMH) tests for pairwise comparisons between groups, and Wilcoxon signed-rank tests for within-group comparisons. Time-to-event data will be analyzed using Cox proportional hazards models or the Kaplan-Meier nonparametric model. Nominal variables will be analyzed using Pearson's chi-square test or, if 25% or more of the cells have expected counts less than 5, Fisher's exact test.

The analyses will include 3 treatment groups: Placebo, 125 U, and 250 U of AGN-151607. Each dose level of AGN-151607 (125 U and 250 U) will be separately compared to placebo. All treatment comparisons will be made at the  $\alpha = 0.05$  level (2-sided). To control for multiplicity in comparing 2 doses of AGN-151607 with placebo, the primary efficacy variable will be tested sequentially by first comparing the high dose to placebo. The low dose will be compared to placebo only if the comparison to the high dose is found to be statistically significant. Details regarding adjustment for multiple comparisons for other efficacy variables will be discussed in the SAP.

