# 9.4.2. Safety Analyses

The safety analysis will be performed using the safety population and will be fully defined in the SAP. The safety parameters will include AEs, physical examination, clinical laboratory tests, vital signs, ECG, pulmonary function, and immunogenicity parameters. For each of physical examination, clinical laboratory, vital sign, and ECG parameters, the last nonmissing safety assessment before the initial dose of treatment will be used as the baseline for all analyses of that safety parameter.

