11.0 Safety Analyses

The safety analysis will be performed using the safety population. The safety parameters will include adverse events (AEs), physical examinations, clinical laboratory test results, vital sign

measurements, electrocardiograph (ECG) results, and pulmonary function testing. For each of the physical examinations, clinical laboratory test results, vital sign measurements, and ECG parameters, the last non-missing safety assessment before the study treatment will be used as the baseline for all analyses of that safety parameter. Continuous variables will be summarized by number of participants and mean, SD, first quartile (Q1), median, minimum, third quartile (Q3), and maximum values. Categorical variables will be summarized by number and percentage of participants.

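### Pulmonary function is meant to be compared between arms, but the SAP plans only by-arm descriptive statistics: no dose-minus-placebo difference, confidence interval or baseline-adjusted model

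*SAP*

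**What the plan says.** SAP 11.5.2 opens with a comparison: "Study participant pulmonary function will be assessed at the screening and day 30 visits using forced procedures and compared across all 3 study groups". Protocol 8.2.5 has the same commitment. The SAP takes both the average and the maximum of the recorded measurements for five parameters (FVC, FEV1, FEV3, FEV6 and the FEV1/FVC ratio). It closes with the only planned output: "Descriptive statistics for each PFT parameter and changes from baseline values at each assessment time point will be presented by treatment group".

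The rule for safety data in SAP 11.0 has the same scope: "Continuous variables will be summarized by number of participants and mean, SD, first quartile (Q1), median, minimum, third quartile (Q3), and maximum values". The safety objective in SAP 5.3 is comparative: "To compare the safety of AGN-151607 with placebo in participants undergoing open-chest cardiac surgery".

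Protocol 9.1 contains a general inferential rule: "Continuous variables will be analyzed using 2-sample t-test or analysis of variance (ANOVA) techniques for comparisons between treatment groups". Protocol 9.4.2, however, hands the safety analysis on: "The safety analysis will be performed using the safety population and will be fully defined in the SAP". Its subsections cover adverse events, laboratory tests, vital signs and ECG, but not PFT. The SAP does not repeat the 9.1 rule for safety data, and SAP 16.0 does not list its absence as a change from the protocol.

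**The concern.** The documents announce a comparison and then give no method for making it. After open-chest surgery, a change from screening to Day 30 within one arm mixes any effect of surgery with any effect of the drug. The informative quantity is each dose minus placebo, and that is what the plan leaves unreported.

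PFT is also the only scheduled test of lung function, done once before treatment and once after. Possible distant spread of toxin is the named event of special interest (Protocol 8.3.6), and 8 of the 40 preferred terms in SAP 11.1 fall under respiratory disorders. Neither document makes PFT part of the distant-spread assessment, so that link is an inference. It does explain why a reader would look for a contrast here.

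At stake is whether the report contains a prespecified PFT difference with an interval. Without one, readers must assemble a difference themselves or judge three columns by eye.

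**Working it through.** **1. The plan's own figures.** The documents give no SD, correlation, margin or power for PFT. The only stated design figure is about 80% power for the primary endpoint with 100 per arm (SAP 13.0: 47.8% against 27.8%, two-sided 0.05). With continuity correction, z = (0.200 − 1/100 − 1.96·√(2·0.378·0.622/100)) / √((0.478·0.522 + 0.278·0.722)/100) = (0.190 − 0.1344)/0.0671 = 0.83, so power is 79.6%. The figure reproduces, and 100 per arm is used below as the upper case for paired tests.

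**2. What the tables allow.** With n, mean and SD of change by arm, anyone can compute the difference in mean change and its standard error √(SD₁²/n₁ + SD₂²/n₂). The proposed adjusted contrast needs the association between screening and Day 30 values within participants, plus each participant's stratum. By-arm tables do not carry the strata. The correlation could be backed out from three SDs only if all three were tabulated on the same paired participants, which the plan does not say.

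**3. Precision.** Let s be the SD of a PFT value, taken as equal at both visits, and r the screening-to-Day-30 correlation. Both are outside the documents, so results are in units of s and r is varied from 0.5 to 0.9.

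- Variance of raw change: 2(1 − r)s²
- Residual variance with screening value as covariate: (1 − r²)s²
- Ratio: (1 − r²)/(2(1 − r)) = (1 + r)/2
- 95% half-width of the difference: 1.96·SD·√(2/n)

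| r | Variance ratio | n = 100: change / ANCOVA | n = 50: change / ANCOVA |
|---|---|---|---|
| 0.5 | 0.75 | 0.277 / 0.240 | 0.392 / 0.339 |
| 0.6 | 0.80 | 0.248 / 0.222 | 0.351 / 0.314 |
| 0.7 | 0.85 | 0.215 / 0.198 | 0.304 / 0.280 |
| 0.8 | 0.90 | 0.175 / 0.166 | 0.248 / 0.235 |
| 0.9 | 0.95 | 0.124 / 0.121 | 0.175 / 0.171 |

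The 50 per arm is an assumption. It is shown because PFT may be waived under local policy with sponsor approval (Protocol 8.2.5 and the Schedule of Activities footnote). The interval narrows by 1 − √0.75 = 13% at r = 0.5 and by 1 − √0.95 = 3% at r = 0.9.

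**4. Chance imbalance.** If the arms differ by d in mean screening value, the raw change difference is displaced by −(1 − r)d, given that imbalance. One standard error of d at 100 per arm is √(2/100) = 0.141 SD, so the displacement is 0.5 × 0.141 = 0.071 SD at r = 0.5 and 0.1 × 0.141 = 0.014 SD at r = 0.9. This is the same gain as in step 3 seen another way, since 2(1 − r) − (1 − r²) = (1 − r)².

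**The case against.** The best defence is consistency. SAP 11.0 sets descriptive summaries for continuous safety variables, and laboratory values, vital signs, ECG and time to extubation are all handled that way. Descriptive safety reporting is common in Phase 2, and three arms side by side is one fair reading of a comparison. This stands in part. It shows that the omission is not peculiar to PFT, and it limits the weight of the point. It does not answer why PFT alone among these parameters carries an explicit promise of comparison across arms. Nor is the model foreign to this SAP: the quality-of-life analysis in 10.4.2 adjusts for baseline and reports differences with intervals.

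A second defence is that Protocol 9.1 already supplies a t-test or ANOVA. Because Protocol 9.4.2 defers to the SAP, this leaves an unreconciled difference between the documents, and the 9.1 rule names no baseline covariate.

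Four stronger readings are tempting and should be resisted:

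- A reader might infer that no upper limit on a PFT loss could be stated. That is wrong, because an unadjusted interval follows from the by-arm statistics.
- A reader might infer that raw change is biased. Under randomisation it is unbiased; the displacement in step 4 of the working is conditional on a chance imbalance, and none is shown.
- A reader might infer that nothing else respiratory is assessed. Respiration rate, the respiratory part of the physical examination, time to extubation and the respiratory adverse-event terms are all covered.
- A reader might infer that monitoring for toxin spread fails. It rests on 40 preferred terms tabulated by arm, and PFT results are also reviewed for clinically significant findings.

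**Conclusion.** The point holds as a gap between what is announced and what is specified. PFT is to be compared across arms, but the SAP plans no difference, interval or baseline-adjusted model, and the protocol's general rule is not carried over. The larger benefit of a correction is that a prespecified comparison gets reported at all. The added precision is modest: a variance ratio of 0.75 to 0.95, which is small if the correlation is high. A low paired n could cost more precision than the covariate recovers. For example, at r = 0.5 the ANCOVA half-width with 50 per arm (0.339 SD) exceeds the raw-change half-width with 100 per arm (0.277 SD).

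These sizes rest on an assumed correlation, equal SDs at the two visits, a normal approximation and assumed numbers of paired tests. The primary efficacy analysis is untouched.

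**What to change.** Add to SAP 11.5.2 a supportive ANCOVA, on the safety population, of Day 30 FVC and FEV1 with screening value, treatment, age group and surgery type. Report each dose minus placebo with a 95% CI. In the same paragraph:

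- Say which of the two existing summaries, average or maximum, leads.
- State that baseline is the screening test. The baseline rule in SAP 11.0 does not list PFT.
- Give the number with paired tests per arm, and reasons for missing Day 30 tests only where already recorded.
- Say how the general rule in Protocol 9.1 applies to PFT, or list the departure in SAP 16.0.

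The cost is SAP wording and one model on values already collected. The downside is four further comparisons (2 parameters × 2 doses) without multiplicity adjustment, to be labelled supportive and read through their intervals. To count as prespecified, the text must be in place before the interim lock, after which SAP 12.0 has sponsor staff unblinded.
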